13.0 Data Collection and Management

The Study Chair and/or her designee, will prepare and maintain adequate and accurate participant case histories with observations and data pertinent to the study. Study specific Case Report Forms (CRFs) will document safety and treatment outcomes for safety monitoring and data analysis. All study data will be entered into OnCore[®] via standardized CRFs in accordance with the CTMS study calendar, using single data entry with a secure access account. The

Clinical Research Coordinator (CRC) will complete the CRFs as soon as possible upon completion of the study visit; the Investigator will review and approve the completed CRFs.

Each participating site will complete study specific CRFs for safety monitoring and data analysis. Each site will enter the study data into OnCore® via standardized CRFs in accordance with the CTMS study calendar, using single data entry with a secure access account. The participating site's Clinical Research Coordinator (CRC) will complete the CRFs; the Investigator will review and approve the completed CRFs – this process must be completed within 3 business days of the visit. Study data from the participating site will be reported and reviewed in aggregate with data from patients enrolled at the coordinating center, UCSF. All source documentation and CTMS data will be available for review/monitoring as needed.

The information collected on CRFs shall be identical to that appearing in original source documents. Source documents will be found in the patient's medical records maintained by UCSF personnel. All source documentation should be kept in separate research folders for each patient.

In accordance with federal regulations, the Investigator is responsible for the accuracy and authenticity of all clinical and laboratory data entered onto CRFs. The Study Chair will approve all completed CRFs to attest that the information contained on the CRFs is true and accurate. All source documentation and CTMS data will be available for review/monitoring by Plexxikon or the designated CRO and regulatory agencies.

The Study Chair will be responsible for ensuring the accurate capture of study data. At study completion, when the CRFs have been declared to be complete and accurate, the database will be locked. Any changes to the data entered into the CRFs after that time can only be made by joint written agreement among the Study Chair, the Trial Statistician, and the Protocol Project Manager.

14.0 Correlative studies

14.1 Tumor biopsies

Tumor biopsies will be obtained from accessible tumor tissue following the guidelines provided below before treatment start in all eligible patients. Patients enrolled on the Phase II trial will be asked to have a second core biopsy or FNA, depending on ease and site of biopsy. Patients who refuse the second biopsy will be allowed to stay on study treatment. Every attempt will be made to obtain tumor tissue at the time of a clinical procedure, if possible. Patients with lung only metastases will not be required to have biopsies, but will be allowed to enroll on this trial.

Core biopsies of the breast will be performed by a qualified radiologist or surgeon, according to institutional guidelines for a diagnostic biopsy. Biopsies of other sites may be done by radiology, pathology or qualified surgeons. When required, radiographic coordination will be arranged. Tissue specimens will be collected from recurrent or metastatic lesions using standard institutional procedures. The goal is to obtain 2 to 4 core needle biopsies using an 18 gauge needle. If a fine needle aspiration is performed, 3-6 passes should be obtained. Less than the goal amount of tissue is acceptable, and should be based upon the clinical judgment of the

Investigator and the clinician performing the procedure. The study coordinator will be present at the time of the biopsy to collect and process the tissue samples. Samples will be delivered to the laboratory of [REDACTED]. Specific processing and delivery instructions will be provided to all sites in the Laboratory Manual, which contains all details for specimen processing and handling.

14.2 CSF1 levels

Patients on both trials will have CSF1 levels drawn to assess the impact of PLX3397. 5 cc of blood will be obtained in a serum separator tube. For patients on the phase I trial, CSF1 levels will be drawn at Cycle 1, days 1 and 2, and Cycle 2, day 1. For patients on the phase II trial, CSF1 levels will be drawn at the start of the PLX3397 lead-in, at day 5 to 7 before the start of eribulin, at Cycle 1, day 1, and Cycle 2, day 1.

14.3 Blood for leukocyte subtyping

Blood will be drawn for flow cytometric analysis at baseline for patients in phase I, and at day -7/5 and day 0/1 for patients on the phase II trial. 10 cc of blood will be drawn into an EDTA tube and evaluated by flow cytometry. Processing will take place at each site. See Lab Manual for more details.

14.4 Pharmacokinetic sampling

Limited pharmacokinetic sampling will be performed in the phase I portion of this trial. PK sampling will occur on C1D1 (pre-PLX3397 administration and at 1, 2, 5, and 24 hours post treatment and on C2D1 (pre-PLX3397 administration and at 2 hours post treatment). Serum concentrations of PLX3397 with eribulin will be assessed by ELISA at Plexxikon Inc. and will be used to calculate the values of PK parameters, including maximum serum drug concentration (C_{max}), area under the concentration-time curve from time zero to infinity (AUC 0-inf), systemic clearance (CL), volume of distribution (V), and elimination half-life (t_{1/2}). Descriptive statistics (including number, mean and/or median, standard deviation, and coefficient of variation) will be used to describe the concentration time data. Where appropriate, these data may be combined with data from other studies as part of a metaanalysis. The influence of exposure on clinical safety parameters (e.g., selected AEs) will be explored. Results of the PK analysis will be evaluated in conjunction with available safety and pharmacodynamic data.

Blood Collection

Approximately 5 mL of blood will be collected via peripheral venipuncture into a lithium heparin tube. This blood sample will be used to measure concentrations of PLX3397 for each PK blood collection, as noted in the Study Calendar. Samples will be collected, processed and stored according to the study-specific laboratory manual.

Blood samples for PK analysis should be collected at the requested time but within a ±15 minute window (or ± 30 minute window where specified) of the requested time. The exact actual time of collection should be noted in the source documents and eCRFs.

Bioanalytical Methodology

The plasma samples will be analyzed for PLX3397 by using a validated method (high performance liquid chromatography (HPLC) with tandem quadruple mass spectrometric detection) of appropriate specificity and sensitivity.

14.5. Archival tumor samples

All patients will be asked to provide a sample of their original tumor pathology, if it is available.

14.6 Details of the correlative studies

The main goal of the correlative studies accompanying this trial will be to identify tissue and serum biomarkers capable of 1) predicting likelihood of response to macrophage-targeted therapy, or 2) providing an early indication of response to PLX3397 treatment likely to be seen at 12 wks of therapy. Both predictive and response biomarker assessment of tissue (core biopsy or FNA) and blood will be conducted as previously described[76, 77]. Phase I studies will be performed on all tumor subtypes, while Phase II studies will be performed on pts with TNBC. The lead-in period in Phase II will allow evaluation of the effect of PLX3397 alone on serum CSF1 levels and leukocyte subsets in blood and tissue prior to administration of eribulin.

14.6.1 Evaluation of baseline biomarkers most likely to predict response to MØ-targeted therapy

We will establish baseline values and variability of immune, and CSF1 measures in pts enrolled in phase I and phase II trials, and correlate these measures to magnitude of change in serum CSF1 levels and clinical response. Pts will be categorized as “good” or “poor” responders based on median change in serum CSF1, clinical response based in RECIST v1.1 imaging criteria at 12 wks and TTP. We will determine whether the tumor phenotype (ER, PR, HER2, and ki67), immune signature (CD68lo/CD4lo/CD8hi vs. CD68hi/CD4hi/CD8lo) and CSF1 signature at initial diagnosis (obtained from archived tumor blocks) correlates with response. In addition, we propose to explore whether the baseline immune and CSF1 signature differ between the early stage setting (derived from ongoing studies) and pts with MBC enrolled on this trial.

14.6.2 Evaluation of dynamic tissue and blood biomarkers most likely to show early biologic changes that predict clinical response

Identify whether leukocyte subpopulations are altered with PLX3397 treatment alone in a cohort of pts with metastatic TNBC. The lead-in design of the trial will allow evaluation of systemic response to PLX3397 alone in the absence of systemic chemotherapy (CTX). We will determine whether this single-agent therapy modulates leukocyte complexity in blood, with serum CSF1 measured between day -7/-5 and day 0/1. In addition, if ongoing studies demonstrates that core biopsy or FNA can reliably recapitulate the immune signature obtained from surgical samples, repeat biopsies will be used to determine whether immune infiltrate in tissue is modulated with PLX3397 treatment. This will provide confirmation that PLX3397 results in the expected macrophage, DC and T cell modulation at the tissue level.

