For Phase II, sample size is based under the Simon's 2-stage optimal design for progression-free survival at 3 months as a single proportion. The study is designed to determine the following hypothesis with >80% power and 2-sided type I error of 5% using binomial approximation: H₀: PFS% <39% versus H_a: PFS% > 57% (with PLX3397), where PFS% is the proportion of progression-free (PFS) at 3 months. The PFS% of >57% would represent a clinically relevant improvement with the treatment in triple-negative patients with locally recurrent or metastatic breast cancer. Based on these considerations, a sample size of 51 evaluable patients is required for the study. We plan for a targeted enrollment of 56 patients with 10% dropout rate.

Interim assessment and stopping rules for Safety and efficacy

Safety and SAE data will be routinely monitored. Because of the possibility of unacceptable or excessive defined serious adverse events during treatment or the study enrollment period, stopping rules for safety/tolerability are also developed. We have set the maximum rate of treatment-related SAE at 15% in patient enrollment. Thus, we may consider terminating the study if the number of patients with SAE is greater than the number expected under the binomial distribution. The following table shows the early stopping guideline based on the number of SAE observed under the rate of unacceptable SAE in the group sequential enrolment for the study. For example, assuming the unacceptable rate of SAE is greater than 15%, if the study observes 3 or more SAE in the first 17 treated patients, then we may consider if the study should be stopped early.

Safety Stopping Rules:

Number of enrolled patients with excessive SAE to consider early study termination.

Number patients in study	1-17	18-29	30-41
Unacceptable SAE – 15%	3	4	6

Efficacy Stopping Rules

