12.7 Correlative studies

Due to the small sample sizes expected from the proposed study design, the correlative studies will be hypothesis generating, but will also help provide pilot data to inform eligibility and follow up of future trials using an MO- \square targeting strategy. CSF1 levels will be analyzed as a continuous variable and categorical variable based on median CSF change with treatment. Mean and 95% confidence intervals of CSF1 levels will be estimated and compared for differences between dose cohorts. As a continuous measure, ANOVA and Pearson correlation will compare CSF1 levels between PLX3389 dose cohorts and response groups. As a categorical measure, Chi-square tests will determine the associations between tumor subtype (molecular profile) and immune profile (dichotomous variable) and between tumor molecular profile and CSF1 groups. FACS analysis of leukocyte populations as a percent of total CD45+ cells will be evaluated among the outcome groups, PFS and ORR. The relationship between mean and median immune infiltrate and continuous quantitative measurements of tumor classification will be reported using either parametric (Pearson) and Fisher's exact tests or nonparametric (Spearman) correlation coefficients and Rank tests and 95% confidence intervals for each statistic.

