14.6.3 Determine magnitude of change in serum CSF1

Determine whether magnitude of change in serum CSF1 is associated with: 1) dose levels of PLX3397 and 2) response to therapy. For patients on the phase I trial, CSF1 levels will be

drawn at Cycle 1, days 1 and 2, and Cycle 2, day 1. For patients on the phase II trial, CSF1 levels will be drawn at the start of the PLX3397 lead-in, at day 5 to 7 before the start of eribulin, at Cycle 1, day 1, and Cycle 2, day 1.. Baseline CSF1 and magnitude of change in CSF1 will be correlated to dose of PLX3397 and treatment response group.

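### Section 14.6.1 correlates baseline CSF1 with a CSF1 change that contains the same baseline value, so an ordinary test against zero can flag baseline CSF1 as a predictor more often than the nominal 5%.

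*Combined protocol and SAP*

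**What the plan says.** Section 14.6.1 opens: "We will establish baseline values and variability of immune, and CSF1 measures in pts enrolled in phase I and phase II trials". It goes on to "correlate these measures to magnitude of change in serum CSF1 levels and clinical response", so baseline CSF1 is one of the quantities set against CSF1 change. The same section sorts patients into good and poor "responders based on median change in serum CSF1", together with RECIST response at 12 weeks and time to progression (TTP).

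Section 14.6.3 adds: "Baseline CSF1 and magnitude of change in CSF1 will be correlated to dose of PLX3397 and treatment response group".

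The second section numbered 12.7 (Correlative studies) also forms CSF1 categories from the median change on treatment. For the continuous measure it says: "As a continuous measure, ANOVA and Pearson correlation will compare CSF1 levels between PLX3389 dose cohorts and response groups". It describes the whole programme this way: "the correlative studies will be hypothesis generating".

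The documents do not say whether change is absolute, percent or log. They describe no adjustment for baseline, no replicate baseline draws and no allowance for regression to the mean.

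**The concern.** Change is computed from the same baseline draw it is being correlated with. A patient whose baseline reads high by chance will tend to show a smaller rise or a larger fall, and one who reads low the reverse. This produces a negative correlation without any biological relation. A test against zero takes zero as the no-relation value, which is wrong for two quantities that share a noisy term. Splitting patients at the median CSF1 change and comparing their baseline CSF1 has the same fault.

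The purpose of 14.6.1 is to find baseline markers that predict response to macrophage-targeted therapy, and 12.7 expects the correlative data to help shape eligibility in later trials. An artefact here could put baseline CSF1 forward as such a marker.

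**Working it through.** **Inputs from the documents.** n=51 comes from 12.1 ("a sample size of 51 evaluable patients is required for the study"), and n=28 for Phase Ib from 12.3. I assume every one of these patients has both samples. The two-sided 5% level is stated in 12.1 for the primary endpoint only, and is assumed here. The plan gives no expected correlation, power or error rate for this analysis, so there is no figure of its own to reproduce.

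**Inputs assumed, because the documents give none.** ρ is the correlation between baseline and follow-up in the same patient. R is the reliability of one baseline measurement. s is the SD of true change, in units of the observed baseline SD.

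**General form.** Let X be baseline, Y follow-up, D = Y − X and k = SD(Y)/SD(X). Then cov(X, D) = cov(X, Y) − var(X), and

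corr(X, D) = (ρk − 1) / √(1 + k² − 2ρk).

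**Case A: equal variances, same true shift in every patient.** With k=1 this becomes −√((1 − ρ)/2):
- ρ=0.5: −√0.25 = −0.50
- ρ=0.8: −√0.10 = −0.32
- ρ=0.9: −√0.05 = −0.22

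**Case B: true change varies between patients, independently of true baseline.** Write X = T + e₁ and Y = T + C + e₂, with var(X)=1 and noise variance 1 − R at each draw. Then D = C + e₂ − e₁, cov(X, D) = −(1 − R), var(D) = s² + 2(1 − R), and

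corr(X, D) = −(1 − R) / √(s² + 2(1 − R)).

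At s=1:
- R=0.8: −0.2/√1.4 = −0.17
- R=0.9: −0.1/√1.2 = −0.09
- R=1.0: 0

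**Rejection rates at n=51**, by simulation of these normal models (60,000 runs, two-sided 5%). The Oldham column correlates change with the mean of the two values, a common substitute.

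| Assumption | Expected r | Baseline vs change (Pearson) | Oldham |
|---|---|---|---|
| A, ρ=0.5 | −0.50 | 97% | 5% |
| A, ρ=0.8 | −0.32 | 63% | 5% |
| A, ρ=0.9 | −0.22 | 35% | 5% |
| B, R=0.8, s=0.5 | −0.25 | 42% | 20% |
| B, R=0.8, s=1 | −0.17 | 22% | 83% |
| B, R=0.9, s=1 | −0.09 | 10% | 87% |
| B, R=1.0, s=1 | 0 | 5% | 92% |

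As a check, the two-sided 5% critical value at n=51 is |r| = 2.01/√(2.01² + 49) = 0.276. An expected r of −0.32 should therefore reject in more than half of trials and −0.22 in fewer than half, as the table shows.

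**Other sizes and methods, case A.**
- Pearson at n=28: about 80%, 39% and 21% at ρ=0.5, 0.8 and 0.9.
- Pearson with both phases pooled (28 + 51 = 79): nearly 100%, 82% and 51%.
- Spearman at n=51: 95%, 58% and 32%, so ranking does not remove the coupling.
- t-test of baseline CSF1 between halves split at the median change, n=51, ρ=0.5: about 85%.

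**The case against.** The strongest reply is that the high rates belong to case A, where all scatter around a common shift is noise. The plan itself looks for CSF1 change that differs by dose and splits patients at the median change, so it expects change to vary. Case B is then the more natural model, and with a precise assay the inflation is small or absent. This stands. A reader might infer that the plan will report baseline CSF1 as a predictor, or usually would. The documents do not support that, because they give none of the quantities that decide it. Equally, nothing in them shows that the trial is in the safe range.

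A reader might also take Pearson to be the named test for this pair. Section 12.7 names it for CSF1 levels against dose cohorts and response groups; 14.6.1 says only that the measures will be correlated. That limits what can be said about the plan's test, but the bias does not depend on the choice between Pearson and rank methods.

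Finally, the work is declared exploratory and no efficacy, safety or stopping decision depends on it. This limits the consequence. Exploratory status excuses low power and multiple looks, but it does not make zero the right null value for this pair.

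**Conclusion.** The concern holds in a limited form. Correlating baseline CSF1 with CSF1 change is biased negative by baseline noise, and the documents contain no safeguard. At n=51, the false-positive rate ranges from about 97% (equal variances, constant shift, ρ=0.5) to the nominal 5% (no measurement noise, true change independent of baseline). Where the trial falls in that range is unknown.

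The effect is confined to this pair and to comparisons of baseline CSF1 across groups defined by CSF1 change, including the response group in 14.6.3 if it is defined that way. Baseline immune measures against CSF1 change, and baseline CSF1 against clinical outcome, share no term and are unaffected. A reader might infer that the primary 12-week result is compromised; it does not use CSF1 and is not touched. The change is worth making because it is nearly free and protects the stated aim of 14.6.1.

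**What to change.** In 14.6.1 and 12.7 (Correlative studies):

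- Remove baseline CSF1 from the measures correlated with CSF1 change, and from comparisons across groups defined by CSF1 change.
- Test baseline CSF1 as a predictor only against outcomes that do not contain CSF1: 12-week progression-free status, RECIST response and TTP.
- Keep the baseline immune measures against CSF1 change as planned.

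Do not substitute the Oldham correlation. It holds 5% only in the equal-variance cases, and rejects in 83% to 92% of trials when true change varies by one baseline SD independently of baseline.

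The cost is a sentence or two of text and the loss of one exploratory correlation. No new samples or patients are needed.

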14.6.3 Determine magnitude of change in serum CSF1

Determine whether magnitude of change in serum CSF1 is associated with: 1) dose levels of PLX3397 and 2) response to therapy. For patients on the phase I trial, CSF1 levels will be

drawn at Cycle 1, days 1 and 2, and Cycle 2, day 1. For patients on the phase II trial, CSF1 levels will be drawn at the start of the PLX3397 lead-in, at day 5 to 7 before the start of eribulin, at Cycle 1, day 1, and Cycle 2, day 1.. Baseline CSF1 and magnitude of change in CSF1 will be correlated to dose of PLX3397 and treatment response group.

15.0 Reporting Adverse Drug Reactions

15.1 Adverse Event Definitions

Adverse Event

An adverse event (also known as an adverse experience) is defined as any untoward medical occurrence associated with the use of a drug in humans, whether or not considered drug related. More specifically, an adverse event (can be any unfavorable and unintended sign (e.g., an abnormal laboratory finding), symptom, or disease temporally associated with the use of a drug, without any judgment about causality. An adverse event can arise from any use of the drug (e.g., off-label use, use in combination with another drug) and from any route of administration, formulation, or dose, including an overdose.

Adverse reaction

An adverse reaction is defined as any adverse event caused by the use of a drug. Adverse reactions are a subset of all suspected adverse reactions for which there is reason to conclude that the drug caused the event.

Suspected

A suspected adverse reaction is defined as any adverse event for which there is a reasonable possibility that the drug caused the adverse event. For the purposes of IND safety reporting, “reasonable possibility” indicates that there is evidence to suggest a causal relationship between the drug and the adverse event. A suspected adverse reaction implies a lesser degree of certainty about causality than an adverse reaction.

Unexpected

An adverse event or suspected adverse reaction is considered *unexpected* if it is not listed in the investigator brochure or package insert(s), or is not listed at the specificity or severity that has been observed, or, if an investigator brochure is not required or available, is not consistent with the risk information described in the general investigational plan or elsewhere in the current application.

“Unexpected,” as used in this definition, also refers to adverse events or suspected adverse reactions that are mentioned in the investigator brochure as occurring with a class of drugs or as anticipated from the pharmacological properties of the drug, but are not specifically mentioned as occurring with the particular drug under investigation.

Adverse events that would be anticipated to occur as part of the disease process are considered *unexpected* for the purposes of reporting because they would not be listed in the investigator brochure. For example, a certain number of non-acute deaths in a cancer trial would be anticipated as an outcome of the underlying disease, but such deaths would generally not be listed as a suspected adverse reaction in the investigator brochure.

Some adverse events are listed in the Investigator Brochure as occurring with the same class of drugs, or as anticipated from the pharmacological properties of the drug, even though they have not been observed with the drug under investigation. Such events would be considered *unexpected* until they have been observed with the drug under investigation. For example, although angioedema is anticipated to occur in some patients exposed to drugs in the ACE inhibitor class and angioedema would be described in the investigator brochure as a class effect, the first case of angioedema observed with the drug under investigation should be considered *unexpected* for reporting purposes.

Serious

An adverse event or suspected adverse reaction is considered *serious* if, in the view of either the investigator or sponsor, it results in any of the following outcomes:

- Death
- Life-threatening adverse event
- Inpatient hospitalization or prolongation of existing hospitalization
- A persistent or significant incapacity or substantial disruption of the ability to conduct normal life function
- Congenital anomaly/birth defect

Important medical events that may not result in death, are life-threatening, or require hospitalization may be considered serious when, based upon appropriate medical judgment, they may jeopardize the patient or subject and may require medical or surgical intervention to prevent one of the outcomes listed in this definition. Examples of such medical events include allergic bronchospasm requiring intensive treatment in an emergency room or at home, blood dyscrasias or convulsions that do not result in inpatient hospitalization, or the development of drug dependency or drug abuse.

Life-threatening

An adverse event or suspected adverse reaction is considered *life-threatening* if, in the view of either the investigator or sponsor, its occurrence places the patient or subject at immediate risk of death. It does not include an adverse event or suspected adverse reaction that, had it occurred in a more severe form, might have caused death.

